CARI Health's long term goal is to develop a minimally-invasive wearable Remote Medication Monitor (RMM) that provides continuous, real-time data on methadone levels in interstitial fluid (ISF). An RMM could be used as a medication adherence monitor and would allow for the physician, counselor, patient, or family member to remotely verify that a physician-prescribed dose has been taken. Such a verification system can allow methadone clinics greater flexibility in the provision of take-home doses and thus retain more patients in opioid treatment programs.

The purpose of this IRB protocol is to evaluate the early safety and feasibility of detecting methadone in the interstitial fluid (ISF) of subjects taking prescribed daily doses of methadone by using a minimally-invasive remote medication monitor (RMM).

We propose the following study aims:

Aim 1: Determine if an RMM can assess the status of taking a prescribed dose of methadone. To complete this aim, the peak and trough concentrations of a witnessed methadone dose will be assessed in ISF collected through the surface of the skin using existing ISF extraction methods and assessed outside the body via differential pulse voltammetry (**DPV**). We hypothesize that the peak and trough blood samples will correlate with the level of methadone in ISF.

Aim 2: Determine if an RMM can continuously assess the status of taking a prescribed dose of methadone over time. To complete this aim, the pharmacokinetic profile of a witnessed methadone dose will be assessed in ISF continuously from the surface of the skin using the RMM for up to 6 hours. We hypothesize that a clinician can recognize a dose taken from the RMM generated measurement of the methadone in the ISF.

C. Background of the Study

Although reported biosensors have been successful in the identification and quantification of several important biomarkers, most of these devices require invasive means to achieve access to blood samples, thus resulting in pain and suffering on behalf of the individual. Furthermore, only a handful of these devices can provide a

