controlled by a microprocessor (MCU). The AFE sets voltages and measures the current between the different types of electrodes (i.e., WE, RE and CE). The DPV waveform consists of an increasing staircase ramp superimposed on a square wave, whereby the waveform parameters (start/end voltage, scan rate, Epulse, Estep, etc) are selected to optimize the performance of the invention. The potentiostat applies the DPV waveform directly across the WE and RE and controls the CE accordingly to generate whatever voltage and current is required to maintain the WE and RE voltages. The electrochemical current that flows from CE to WE (or vice versa) is relayed to the Bluetooth Low Energy Communication Module module for transmission to a smartphone or laptop.

Initial studies of the microneedle sensor device have been performed in the lab for demonstration of sensing methadone/EDDP levels in artificial ISF [list of prior studies provided below]. Attractive performance was achieved non-enzymatically using a proprietary coating over platinum microneedle electrodes. Thus, the microneedle sensor device can be readily expanded toward realization of real-time, on-body testing on humans to offer useful insights into patients daily dosing of methadone.

Additional prior relevant studies and references include:

- Toxicity level of the microneedle coating material based on standard and independent cytotoxicity studies (see attached cytotoxicity report from Nelson showing the EAC1 coating used in our assay is not cytotoxic).
- Methadone in ISF (see attached clinicaltrials.gov results and Enzyme official study reports).
- Data on the ability of the proprietary assay to quantitatively detect methadone and EDDP
- Related work by others [15] showing proof of concept in humans for phenylalanine dose taken, and reference [16] for tylenol dose taken

PARTICIPANT SELECTION

D. Inclusion and Exclusion Criteria

Aim 1 and 2 (up to N = 20):

- **Inclusion criteria for methadone group includes:**
 - o Age 18-70.
 - o A prescription for methadone for chronic pain at a dose of 10mg or more for at least one week.
 - o Taking methadone as prescribed during the last 4 days before consent to participate in the study.
- **Exclusion criteria for methadone group includes:**
 - o Age <18 or >70.
 - o A condition preventing or complicating ISF collection
 - o Conditions may include dermatological (skin) condition
 - o bleeding diathesis
 - o immunodeficiency
 - o recent blood donation
 - o anemia

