We will conduct a non-randomized, non-blinded, feasibility study at a single center in the United States. The study will include up to 20 subjects of an equal number of male and female adults (ages 18–70) who have a prescription for methadone for chronic pain. In **Aim 1**, we will determine if an RMM can assess the status of taking a prescribed dose of methadone, using biosamples (i.e., ISF, blood) collected from subjects and tested in a laboratory setup. Biosample collections and pharmacokinetic monitoring will take up to 6 consecutive hours. By completing this aim, we will determine if a physician is able to recognize the peak and trough concentrations of a witnessed methadone dose by DPV or LC-MS data using one of the three available ISF extraction methods described later in this protocol (i.e., Samplimy, Kiffik, or Prausnitz). In **Aim 2**, we will determine if an RMM can continuously assess the status of taking a prescribed dose of methadone over time, by inserting the intradermal microneedle sensing elements of the RMM in the subjects’ skin. The electronics for the RMM prototypes will consist of commercially-available benchtop potentiostats like the PalmSens Sensit BT (<https://www.palmsens.com/product/palmsens4/>) or CH Instruments 660D (<https://www.chinstruments.com/>) and will not be in direct contact with the skin. Biosample collections (i.e., ISF, blood) and pharmacokinetic monitoring will occur over a 6 hour period. By completing this aim, we will determine if a physician is able to recognize a pharmacokinetic profile of a witnessed methadone dose via data collected using intradermal microneedle sensing elements worn continuously on the skin. Completion of Aims 1-2 will require two separate visits.

A. Summary of the Research Design for Aims 1-2

Subject Recruitment Strategy: Up to 20 adults ages 18-80 years of age will be recruited to participate in this study. Subjects will be recruited from pain management clinics and primary care physicians providing control of chronic pain with methadone prescriptions. Human subjects research will be performed at Synergy Research Centers (<https://www.synergypainresearch.com>) in San Diego which is a well-established clinical trial company that provides appropriate staff and facilities to conduct this study.

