 - Diet and exercise habits
 - Tobacco, alcohol and other substance use history
 - Previous pregnancy history (if female)
- The CRC will schedule an in-person clinical visit for the subjects if needed. Subjects will be instructed to take their medications as prescribed by their physician (e.g., dose, dosing times). As such, the in-person visits will be scheduled around the subjects usual dosing time. Subjects will also be asked to abstain from alcohol and non-prescribed substances at least 24 hours before their in-person assessment.

- **In-person study visit within 7 days after the initial consent and online assessment is completed:**

- **Physical assessment (up to 30 minutes; Aims 1-2)**

- The in-person assessment may include the following:

1. Limited physical exam:
 - Height and weight measurements
 - Feeling for the pulse
 - Listening to the heart and lungs with a stethoscope
 - Measuring blood pressure using a sphygmomanometer
2. Changes in medications in the past week
3. Use of substances (e.g., opioids, alcohol) in the past week
4. Urine toxicology test to confirm no other substance use

- b. **Prescribed dose of medication (5 minutes; Aims 1-2)**
 - i. Participants will be asked to take their prescribed methadone medication at the study site. Study personnel shall observe that a dose has been taken.
- c. **Blood sample collections (5 minutes each; Aims 1-2)**
 - i. At medication peak and trough, a standard venipuncture blood sample will be collected by a certified clinician. These samples will be used for comparative analysis with the sensor's ISF Methadone Readings and LC-MS assays of the extracted ISF samples.
- d. **Visit 1 ISF samples collected by 1 of 3 potential methods.**
 - 1. ISF is collected from subjects using one or more of three published extraction methods (i.e., Samplimy, Kiffik, or Prausnitz). The subject is asked for a preference of location (dorsal side of right or left upper arm, or alternatively ventral side of right or left forearm) and the clinician applies the appropriately selected method to collect ISF. If more than one of the three ISF collection methods are applied then it will be applied on the same upper arm or forearm areas by the physician at least 10 cm apart. Participants will have the opportunity to decide whether they are willing to have more than one of the extraction methods administered.

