 - a. **Samplimy Method** (microneedle patch and applicator as per (Ribet et al., 2023)): First applied 1 hour prior to dosing and continued every 15-30 minutes until 4 hrs after dosing (total of 5 hours). An applicator will ensure consistent control of the force and speed of attaching the intradermal microneedle and the pressure required for microneedle extraction [17].
 - a. **Prausnitz Extraction Method** (manual microneedle application): As described in our IRB 002 (#20222142) approved and completed study, a minimally invasive microneedle array will be used in conjunction with a standard vacuum pump. Microneedles (without the patch) will be inserted and removed multiple times (~10) to collect about 1 μ l of ISF. This approach has been well tolerated with faint visual evidence of micropores in the skin in previous studies, including ours [18].
 - b. **Kiffik Method:** A certified physician will place the Kiffik device on the participant's preferred arm. ISF collection will start 2 hrs prior to taking the participant prescribed methadone dose and will end prior to dosing with repeat collections after dosing every 2 hrs until 6 hrs of collection time has ended. Thus, a total of 3 samples will be collected from each participant [19].
- e. **Visit 2 ISF samples collected by 1 of 3 potential methods .**
 - i. The steps listed above (section d #1) will be repeated for visit two (Aim 2), however, in addition to having ISF collected from the skin, the subject will also be applied with up to 3 RMM device(s) and continuously wear them for up to 6 hours. This will replicate how other standard of care continuous monitoring devices (e.g. CGMs) are worn (e.g., <https://www.niddk.nih.gov/health-information/diabetes/overview/managing-diabetes/continuous-glucose-monitoring>). The continuously monitored levels will be compared to the ISF extracted levels as well as the peak and trough blood levels as explained in the analysis section of this protocol.
 - f. The RMM device will consist of a microneedle sensor array wired to a benchtop potentiostat like the PalmSens Sensit BT or CHI 660D. Data will be continuously collected using either bluetooth or data cables. Computer programs will be used to record, measure and analyze methadone and its metabolite levels in the collected sample data. The resultant Differential Pulse Voltammograms will be translated into pharmacokinetic data and securely stored for analysis by the lead research staff.

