 - g. Up to 6 hrs after the application is complete, the microneedles will be removed, the insertion area inspected and a sterile bandage covering will be supplied to the area.

- h. Subjects will be monitored before, during, and 15 minutes after the application to report their tolerability, pain, and experience. Their responses will be documented on a secured google drive spreadsheet, which will be encrypted with a password that adheres to secure GCP certified online storage medium requirements.

- **Method of sample preservation**

- a. Blood samples will be centrifuged and plasma will be kept in the refrigerator.
- b. Collected ISF samples using the single hollowed microneedle with absorbent paper devices will be prepared as outlined by Bird Rock Laboratories and [name] (developer of the Samplimy method).
- c. Collected ISF samples will be analyzed at the time of study and frozen after analysis
- d. All samples will be transported to the laboratory within 7 days of collection and stored in the refrigerator.

- **Follow-up call/visit (15 minutes)**

- a. Approximately 2 days after the microneedle application, subjects will be contacted by the CRC via phone. Subjects will be asked to report their tolerability, pain, and experience. Their responses will be documented in a secure online storage medium.

- **Compensation:**

- a. **Day 1 (Aim 1):** Subjects participating in the first part of this study will be compensated with an online visa gift card worth up to \$250 for their participation. Subjects will be compensated \$25 for the initial online assessment (up to 15-30 minutes), \$25 for the in-person physical exam (up to 30 minutes), \$130 ISF sample collections (up to 6 hours), \$50 using the standard venipuncture with vacuum tube based blood collection (1 pre and 1 post sample per day), and \$20 for the follow-up call (up to 15 minutes).
- b. **Day 2 (Aim 2):** Subjects participating in the second part of this study will be compensated with an online visa gift card worth up to \$250 for their participation subjects will be compensated \$25 for the online assessment (up to 15-30 minutes), \$25 for the in-person physical exam (up to 30 minutes), \$130 for ISF sample collection, continuous sensor application, and data collection (up to 6 hrs), \$50 using the standard venipuncture with vacuum tube based blood collection (1 pre and 1 post sample per day), and \$20 for the follow-up call (up to 15 minutes).

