ISF samples collected using the Samplimy or Kiffik method will be assessed using the RMM in the same way that they will be assessed in vivo but with modifications as outlined in the phenylalanine dose taken example study.

Concentration determinations from analyte peaks in the Voltammograms will be correlated to the trough and peak blood methadone levels.

All samples will be safely stored and processed according to Good Clinical Practice Guidelines. None of them will be used for any DNA analysis.

C. Monitoring

N/A

D. Storage of Data

The original electronically signed consent forms will be stored in a secure password protected file online via the Adobe Sign BA agreement based Storage Service. Only the research team members (Principal Investigators/Co-Investigators) and the CRCs will have access to identifiable private information.

An electronic data sheet casebook using GCP certified software will be used for each subject enrolled in the study. The appropriate data sheet will be completed online by the CRCs after each visit. All data collected for the study will be reviewed for quality assurance, data entry, and statistical analysis. All electronic forms will be reviewed for completeness; evident recording errors will be rectified by contact with the appropriate clinical staff. All data sheets will be reviewed by a research team member before final data entry submission. Laboratory Data will be entered within two (2) weeks of a receipt from the independent laboratory. Any corrections will be made electronically.

All biological samples will be stored and processed through standard IRB approved procedures. Subjects will consent to allow their deidentified biological samples to be stored for future use.

All team members will be GCP certified and trained to protect identifiable private information (e.g., signed consent). Deidentified research data will be kept separate from identifiable data in secure GCP certified online locations for the duration of the study. This protocol was designed and will be conducted, recorded, and reported in compliance with the principles of GCP regulations. These requirements are stated in global regulations as well as "Guidance for Good Clinical Practice," International Conference on Harmonization (ICH), and the most recent guidelines of the Declaration of Helsinki of Technical Requirements for Registration of Pharmaceuticals for Human Use.

E. Confidentiality of Data

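### Aim 1's only stated hypothesis is an ISF-blood correlation that differences between people can drive, so a reading that does not follow the dose could still appear to support it

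*Protocol*

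**What the plan says.** The study aims section of the protocol sets Aim 1 as: "Determine if an RMM can assess the status of taking a prescribed dose of methadone". The hypothesis attached to it is: "We hypothesize that the peak and trough blood samples will correlate with the level of methadone in ISF". No other hypothesis is given for Aim 1.

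Section B, Analysis of Study Results, repeats this for the sensor: "Concentration determinations from analyte peaks in the Voltammograms will be correlated to the trough and peak blood methadone levels". The blood-sampling step of the study procedures gives the purpose of the draws: "These samples will be used for comparative analysis with the sensor's ISF Methadone Readings and LC-MS assays of the extracted ISF samples". The Visit 2 step sends its comparison to the same place, since the continuous readings are to be "compared to the ISF extracted levels as well as the peak and trough blood levels as explained in the analysis section of this protocol".

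Three design facts bear on the point:

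- Eligibility requires "A prescription for methadone for chronic pain at a dose of 10mg or more for at least one week", with no upper limit.
- Sample size: "The study will include up to 20 subjects of an equal number of male and female adults".
- Blood draws, from the compensation items: "1 pre and 1 post sample per day".

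Section B also describes a separate route to the dose-taken decision. A physician uses the individual's ISF slope from 2 to 4 hours after a witnessed dose, and may use an individual AUC ratio. The study design section describes completing Aim 1 as finding out whether a physician can recognise the peak and trough of a witnessed dose.

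**The concern.** Taking a dose is an event within a person, so the relevant signal is the difference between that person's readings before and after it. A correlation computed across people mixes that signal with standing differences in level caused by dose and clearance. If the standing differences are large, the coefficient mainly reports whether people with high blood levels also have high sensor readings. A sensor can do that well without registering the dose just taken.

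At stake is how Aim 1 is reported. A high r would match the stated hypothesis even if readings before and after the dose did not differ within anyone. The up to 40 trough and peak values per visit (20 people × 2) are also 20 dependent pairs, so a naive p-value or interval for r would not be valid.

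**Working it through.** **Nothing to reproduce.** The protocol gives no expected correlation, threshold, alpha or power. The check asks how large r becomes when the sensor has no trough-to-peak response.

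**Inputs from the protocol.** Up to 20 subjects; one trough and one peak blood sample per visit; dose at least 10 mg with no maximum.

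**Assumptions, not in the protocol.** Between-person log-SD of concentration s_b = 0.2 to 0.8; peak/trough ratio R = 1.3 to 2.0, the same for everyone, with d = ln R; sensor noise log-SD s_e = 0.2. For scale, doses spread log-uniformly over a k-fold range give s_b = ln(k)/√12, which is 0.20, 0.40, 0.60 and 0.80 for k = 2, 4, 8 and 16.

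**Model on the log scale.** Blood is m_i − d/2 at trough and m_i + d/2 at peak, where m_i is the person's standing level. The flat sensor reads m_i plus noise at both times.

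- Flat sensor, trough and peak pooled: r = s_b² / [√(s_b² + d²/4) · √(s_b² + s_e²)]
- Flat sensor, trough with trough or peak with peak: r = s_b / √(s_b² + s_e²)
- Sensor that follows blood, pooled: r = √[V/(V + s_e²)], with V = s_b² + d²/4

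Examples for the flat sensor:

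- s_b = 0.4, R = 2.0: d²/4 = 0.120, so r = 0.16/(√0.280 × √0.200) = 0.16/0.237 = 0.68.
- s_b = 0.8, R = 1.3: d²/4 = 0.017, so r = 0.64/(√0.657 × √0.680) = 0.64/0.669 = 0.96.
- s_b = 0.2, R = 2.0: r = 0.04/(√0.160 × √0.080) = 0.04/0.113 = 0.35.

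| s_b | Flat, pooled (R = 1.3 / 2.0) | Flat, separate | Follows blood, pooled (R = 1.3 / 2.0) |
|---|---|---|---|
| 0.2 | 0.59 / 0.35 | 0.71 | 0.77 / 0.89 |
| 0.4 | 0.85 / 0.68 | 0.89 | 0.90 / 0.94 |
| 0.6 | 0.93 / 0.82 | 0.95 | 0.95 / 0.96 |
| 0.8 | 0.96 / 0.89 | 0.97 | 0.97 / 0.97 |

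**Simulation.** Raw-scale Pearson r with 20 people agrees. Over s_b = 0.4 to 0.8 the median pooled r is 0.65 to 0.94 for the flat sensor and 0.89 to 0.97 for the true one. At s_b = 0.2 the flat sensor gives 0.35 to 0.57. A wide dose range is not required: with one common dose and a pharmacokinetic log-SD of 0.4, the flat sensor gives 0.65 to 0.78 at ratios of 2.0 and 1.5. With one common dose and no pharmacokinetic variation, r is about 0. A sensor blind to methadone gives about 0 throughout.

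**Within-person measures under the same model.**

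- Repeated-measures correlation: for the true sensor it is about d/√(d² + 2s_e²), that is 0.262/√(0.069 + 0.080) = 0.68 at R = 1.3 and 0.693/√(0.480 + 0.080) = 0.93 at R = 2.0. Simulation gives 0.69 to 0.93 for the true sensor and about 0 for the flat one.
- Mean paired change: its SD per person is √2 × 0.2 = 0.283. With 20 people the 95% half-width is 2.093 × 0.283/√20 = 0.13. The expected change is 0 for the flat sensor and 0.26 to 0.69 for the true one. In simulation a paired t-test requiring a rise passed the flat sensor in about 2 to 3.5% of runs. It passed the true sensor in about 100% at ratios of 1.5 to 2.0.
- Correlating change with change across people fails. It is undefined if everyone has the same ratio, and reached only about 0.48 for a true sensor with modest variation in the ratio.

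**The case against.** The strongest reply is that the protocol already contains a within-person analysis. Dose-taken status is decided by a physician from the individual's ISF slope or AUC ratio, and a flat sensor would show no systematic slope however high r is. This stands. A reader might infer that the correlation can produce a false positive on whether a dose was taken; the protocol does not support that, because r does not make that decision. But the slope judgement uses ISF alone and is not linked to the correlation, so it does not repair the hypothesis stated for Aim 1.

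Second, a reader might infer that the plan pools trough and peak values as 40 independent points and tests r. The protocol says none of this and sets no threshold, and an analysis plan not shown could specify a repeated-measures form. Pooling is only the natural reading. The fault does not depend on it, since separate trough and peak correlations reach 0.89 at s_b = 0.4. The hypothesis and the measure are fixed in the protocol itself.

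Third, the flat sensor is an extreme case: it reads standing level well and ignores only the change. A blunted or delayed ISF response is more realistic and was not simulated. The size also depends on a between-person spread that the protocol does not state. Both limits stand.

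**Conclusion.** The concern holds in a limited form. The one hypothesis and the one sensor-blood analysis stated for Aim 1 do not isolate the within-person change that Aim 1 is about. Where between-person spread is moderate to large (log-SD 0.4 to 0.8), a sensor that does not follow the dose gives a median pooled r of about 0.65 to 0.94, against 0.89 to 0.97 for one that does. The coefficient then separates the two poorly, most of all when the peak/trough ratio is small. With little spread (log-SD 0.2) the spurious value is about 0.35 to 0.57.

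All these figures rest on the assumed spread, peak/trough ratio and 20% noise. The consequence is that the Aim 1 hypothesis could be reported as supported when the sensor does not follow the dose. The physician's dose-taken determination is not itself shown to be wrong.

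**What to change.** In the Aim 1 hypothesis and in Analysis of Study Results, state as the main sensor-blood analysis:

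- the mean within-person trough-to-peak change in log DPV/ISF concentration with its 95% CI, shown beside the same change in blood; and
- a repeated-measures correlation, or a mixed model with a participant effect.

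Pair each blood draw with the nearest ISF or RMM reading or, where a method collects over an interval (the Kiffik method works in 2-hour steps), with the nearest collection interval. Do not rely on correlating change with change across people. Keep the overall correlation as descriptive.

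The cost is a few sentences and a little more analysis, with no new samples or visits. The reported correlation may be less favourable.
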